#### **10.4.1.3 Adverse event of special interest**

An adverse event of special interest (AESI) is an AE (serious or non-serious) that needs to be monitored, documented, and managed in a pre-specified manner described in the protocol.

For this study, the AESIs are the following (refer also to [Section 10.4.4](#) for the reporting time frame, and the corresponding complementary forms in the e-CRF to be filled):

- **Increase in alanine aminotransferase (ALT):**
  - ALT  $\geq 3 \times$  ULN (if baseline ALT  $<$ ULN) or ALT  $\geq 2$  times the baseline value (if baseline ALT  $\geq$ ULN) (Please refer to related flowchart in [Appendix F](#)).
- **Allergic events that require consultation with another physician** for further evaluation of hypersensitivity/allergy as per the Investigator's medical judgment.
- **Local injection site reactions that are allergic in nature:**
  - Local injection site reactions deemed to be allergic by the Investigator (or have an allergic component) and that require consultation with another physician for further evaluation of hypersensitivity/allergy as per the Investigator's medical judgment should be reported as AESIs.

Note: Other local injection site reactions are non-AESIs. Please see [Section 10.4.1.4](#) for details.

Note: The safety instructions on allergic events and local injection site reactions are detailed in [Section 10.6](#).
- **Pregnancy:**
  - Pregnancy occurring in a female patient or the female partner of a male patient (if data collection is permitted by the female partner and by local regulatory authorities) during the study or within 70 days (10 weeks) following the last dose of IMP.
  - Pregnancy will be recorded as AESI in all cases. Pregnancy will be qualified as an SAE only if it fulfils one or more SAE criteria.
  - In the event of pregnancy of a female patient included in the study, the IMP should be permanently discontinued.
  - The follow-up of the pregnancy will be mandatory until the outcome is determined.
- **Symptomatic overdose with IMP:**
  - An overdose (accidental or intentional) is an event suspected by the Investigator or spontaneously notified by the patient (not based on systematic injection counts) and defined as at least twice of the intended dose within the intended therapeutic interval (ie, 2 or more injections of the study treatment are administered in  $<7$  calendar days). The symptomatic overdose should be reported using the term "symptomatic overdose (accidental or intentional)", indicating the circumstance in parentheses (eg, "symptomatic overdose [accidental]" or "symptomatic overdose [intentional]"). The patient should be monitored and appropriate symptomatic treatment instituted,
  - The circumstances of the overdose should be clearly specified in the verbatim, and the symptoms, if any, entered on separate AE/SAE forms,
  - Of note, asymptomatic overdose should be reported as a standard AE.

- **Neurologic events:**
  - Neurologic events that require additional examinations/procedures and/or referral to a specialist should be reported as an AESI. If the event does not require additional examinations/procedures and/or referral to a specialist, it should be reported as a standard adverse event.
- **Neurocognitive events:**
  - All neurocognitive events will be considered as AESI.

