h.	Safety evaluation: Adverse Events (AEs), product complaints, regardless of seriousness or relationship to alirocumab treatment, will be collected from the time the patient signs the informed consent form up to the EOT/EOS visit																	
i.	Review patient diary and treatment kit +data collection on study treatment administration.																	
j.	Repeat lab only in case of abnormality at EOT/EOS.																	
k.	New kit dispensation only if needed as per lab results.																	
l.	Hepatitis C only.																	
m.	Serum pregnancy test.																	
n.	Urine pregnancy test.																	

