**10.1.2.5 End-of-treatment (EOT/EOS) visit: Visit 17 / Week 120 (Day 841 +7)**

This EOT/EOS visit should occur at least 14 days (+7 days) after last injection (ie, within a 14-21 days' time window).

This visit may occur before Week 120 if the commercial alirocumab (Praluent) becomes available before this date in a given country.

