#### **10.4.2 General guidelines for reporting adverse events (and product complaints)**

- All AEs, regardless of seriousness or relationship to investigational medical product (IMP)/ non investigational medical product (NIMP), spanning from the signature of the informed consent form until the end of the study as defined by the protocol for that patient, are to be recorded on the corresponding page(s) or screen(s) of the CRF.
- All products complaints associated or not to an AE are to be recorded immediately on the corresponding products (study medical device) complaints pages and reported to local Complaint Service immediately (within 24 hours).

- Whenever possible, diagnosis or single syndrome should be reported instead of symptoms. The Investigator should specify the date of onset, intensity, action taken with respect to IMP, corrective treatment/therapy given, additional investigations performed, outcome, and his/her opinion as to whether there is a reasonable possibility that the AE was caused by the IMP or by the study procedure(s).
- The Investigator should take appropriate measures to follow all AEs until clinical recovery is complete and laboratory results have returned to normal, or until progression has been stabilized, or until death, in order to ensure the safety of the patients. This may imply that observations will continue beyond the last planned visit per protocol, and that additional investigations may be requested by the monitoring team up to as noticed by the Sponsor.
- Patients who experience an ongoing SAE or an AESI, at the prespecified study end-date, should be followed until resolution, stabilization, or death and related data will be collected. The duration of post study follow-up and reporting of AEs will be specified (eg, until recovery).
- When treatment is prematurely discontinued, the patient will have an EOT (=EOS) visit at least 2 weeks after the last study treatment injection unless there is an AE to be followed until final outcome and related data will be collected.
- Laboratory or vital signs are to be recorded as AEs only if:
  - Symptomatic and/or,
  - Requiring either corrective treatment or consultation, and/or,
  - Leading to IMP discontinuation or modification of dosing, and/or,
  - Fulfilling a seriousness criterion, and/or,
  - Defined as an AESI.

Instructions for AE reporting are summarized in [Appendix E](#).

- Adverse event (injection site reactions) recorded in patient's questionnaire:  

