## Appendix E    Summary of Adverse Events reporting instructions at Sanofi

[figure not shown]
EVENT CATEGORY	REPORTING TIMEFRAME	SPECIFIC EVENTS IN THIS CATEGORY	CASE REPORT FORM COMPLETION		
			AE form	Safety complementary Form a	Other specific forms
Adverse event (non-SAE, non-AESI)	Routine	Any AE that is not SAE or AESI	Yes	No	No
Serious Adverse Event (non-AESI or AESI)	Expedited (within 24 hours)	Any AE meeting seriousness criterion per Section 10.4.1.2	Yes	Yes	No, unless applicable
Adverse Event of Special Interest (AESI)	Expedited (within 24 hours)	Pregnancy of female patient/subject (including male subject's partner as described in Section 10.4.1.3 )	Yes	Yes	Yes
		Symptomatic overdose with IMP	Yes	Yes	No
		Increase in ALT as follows: - ALT $\geq 3$ ULN (if baseline ALT <ULN) or - ALT $\geq 2$ times the baseline value (if baseline ALT $\geq$ ULN) Please refer to related flowchart (per Appendix C )	Yes	Yes	Yes
		Allergic drug reactions and/or local injection site reactions deemed to be allergic and requiring consultation with another physician as specified in Section 10.4.1.3 .	Yes	Yes	Yes b
		Neurologic events (requiring additional examinations/procedures and/or consultation with a specialist as specified in Section 10.4.1.3 )	Yes	Yes	Yes
		Neurocognitive events ( Section 10.4.1.3 )	Yes	Yes	Yes
		Non-allergic or allergic not requiring consultation with another physician, as described in Section 10.4.1.4 .	Yes	No	Yes b
Local injection site reaction	Routine				

EVENT CATEGORY	REPORTING TIMEFRAME	SPECIFIC EVENTS IN THIS CATEGORY	CASE REPORT FORM COMPLETION		
			AE form	Safety complementary Form a	Other specific forms
Laboratory or vital sign abnormality (non-SAE, non-AESI) that is: - Symptomatic - Requiring corrective treatment or consultation - Leading to IMP discontinuation or dose regimen modification	Routine	- Neutropenia - Thrombocytopenia - Acute renal insufficiency - Increase in CPK and suspicion of rhabdomyolysis Per Appendix C .	Yes	No	No

- a. Completion of a Safety Complementary Form is required for any AE meeting a seriousness or AESI criterion, even if this is not otherwise required according to the table for a particular type of AE

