- In addition, an analysis will be performed for any local injection site reaction not meeting AESI criteria (not allergic and not requiring consultation with another physician) using the HLT “injection site reaction”.
- **Pregnancy** of female patients will be selected using the appropriate MedDRA codes.

- **Symptomatic overdose with Alirocumab.** Overdose with alirocumab is defined as at least twice of the intended dose within the intended therapeutic interval (ie, 2 or more injections are administered in <7 calendar days), to be reported using the Term “symptomatic OVERDOSE” (accidental or intentional), indicating the circumstance in parentheses (eg, “symptomatic overdose [accidental]” or “symptomatic overdose [intentional]”). These events will be selected using the AESI category as selected by the site.
- Another analysis will be performed using all overdose cases (whether symptomatic or asymptomatic and whether with alirocumab or another drug) using the HLT “Overdose”.
- In addition, an analysis will be performed using all overdose cases (whether symptomatic or asymptomatic) using the HLT “Overdose” with the condition “relationship to investigational medicinal product (IMP)” as YES.
- **Neurologic events that require additional examinations/procedures and/or referral to a specialist** will be selected using SMQ “demyelination” (broad and narrow), “peripheral neuropathy” (broad and narrow), and “Guillain Barre syndrome” (broad and narrow) excluding the following preferred terms: “acute respiratory distress syndrome”, “asthenia”, “respiratory arrest”, and “respiratory failure”.
- An additional analysis will be performed analyzing all events meeting the above SMQ criteria for neurologic events whether or not the criteria for an AESI are met (whether or not requiring additional exams/procedures and/or referral to a specialist).
- **Neurocognitive events** will be selected using the sponsor Company MedDRA Query (CMQ) based on HLTs “Deliria (incl confusion)”, “Cognitive and attention disorders and disturbances”, “Dementia and amnestic conditions”, “Disturbances in thinking and perception”, “Mental impairment disorders”.

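### The protocol's pregnancy AESI covers male patients' partners and runs to 70 days after the last dose; the SAP selects female patients only, and nothing plans ascertainment after EOT/EOS

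*Protocol*

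**What the plan says.** **Definition.** Protocol 10.4.1.3 defines the AESI as "Pregnancy occurring in a female patient or the female partner of a male patient", subject to the partner's and local authorities' permission for data collection, "during the study or within 70 days (10 weeks) following the last dose of IMP". It is to be recorded as an AESI in every case and followed to outcome. The reporting table in Appendix E repeats the partner clause ("including male subject's partner as described in" Section 10.4.1.3) and requires notification within 24 hours.

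**Collection.** Flow chart note h says that adverse events "will be collected from the time the patient signs the informed consent form up to the EOT/EOS visit". Section 10.1.2.5 states "This EOT/EOS visit should occur at least 14 days (+7 days) after last injection" and glosses this as "within a 14-21 days' time window". Section 10.4.2 has adverse events recorded over a period "spanning from the signature of the informed consent form until the end of the study as defined by the protocol for that patient". Section 6.2.1 ends the study for a patient at the last planned visit, at resolution or stabilisation of SAEs and AESIs, or at death, whichever is latest. The last scheduled pregnancy test is at EOT/EOS. Appendix K collects pregnancies of patients and partners that begin during participation and mentions no 70-day period.

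**Analysis.** SAP 2.1.4.1 says that AESIs will be analysed as the amended protocol defines them. It then states that pregnancy "of female patients will be selected using the appropriate MedDRA codes". Neither SAP 1.5 nor SAP 1.6 declares a narrowing of this AESI.

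**The concern.** Safety is the primary endpoint, and the protocol summary names AESIs as part of it. For this AESI the definition, the collection rules and the analysis cover different people and different periods.

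Two things are at stake. A programmer who follows the SAP would select no partner pregnancies, although sites must report them within 24 hours. And a reader of the study report would take a pregnancy count, possibly zero, to apply to the defined window, when the later part of that window rests on sites happening to hear of a pregnancy. With an event likely to be rare, one or two cases could be most of the data.

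**Working it through.** No alpha, power or sample size enters. The check is a comparison of passages plus day arithmetic.

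**Inputs**
- AESI window: 70 days after the last dose (Protocol 10.4.1.3)
- EOT/EOS: 14 days, +7 days, after the last injection (Protocol 10.1.2.5)
- End of adverse event collection: EOT/EOS (Protocol 1.2, note h)
- SAP selection: female patients (SAP 2.1.4.1)

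**The plan's own figures reproduce.** 70 / 7 = 10 weeks; 14 + 7 = 21 days.

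**Part of the window after the last scheduled contact.** If EOT/EOS falls on day v after the last injection, the gap is 70 − v days.
- v = 21: 70 − 21 = 49 days; 49/70 = 70%
- v = 14: 70 − 14 = 56 days; 56/70 = 80%

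Protocol 6.1, 6.2.1 and 10.3.2.2 give only the two-week minimum with no upper limit, so a later visit would shorten the gap. It is zero for a contact at day 70. SAP 1.5 describes a 10-week visit under the original protocol for premature discontinuers and for patients switching to another compound. SAP Table 3 keeps a window for it of 10 ± 4 weeks, that is, day 70 − 28 = 42 to day 70 + 28 = 98. The 49 to 56 days therefore do not describe those patients.

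**What covers the gap?**
- *A pregnancy known by EOT/EOS* is an open AESI. Section 6.2.1 keeps the patient in the study and Section 10.4.1.3 requires follow-up to outcome. Recording is unclear: Section 10.4.2 says data on ongoing AESIs will be collected, while the triple-asterisk note to the flow chart says nothing more is entered in the eCRF.
- *A pregnancy first arising after EOT/EOS and by day 70* meets the AESI definition, and Section 10.4.4 would have it notified within 24 hours if the site learned of it. No visit, call or test is scheduled to detect it. Section 10.4.3 covers post-study events only when they are SAEs judged caused by the IMP, and Section 10.4.1.3 makes a pregnancy an SAE only if it meets a seriousness criterion.
- Appendix K adds a further conflict. It says pregnancy itself is neither an AE nor an SAE, while Section 10.4.1.3 records it as an AESI in all cases.

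**Who is analysed?**

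| Source | Female patient | Partner of male patient |
|---|---|---|
| Protocol 10.4.1.3, Appendix E | AESI | AESI |
| SAP 2.1.4.1 | selected | not selected |

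For allergic, injection-site, overdose and neurologic events, SAP 2.1.4.1 adds analyses broader than the AESI definition. For pregnancy it goes below it.

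**The case against.** A reader might infer more than the documents support, on four counts.

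- **That the count must be incomplete, or that 70% to 80% of pregnancies are lost.** The figure is a share of days. The documents give no pregnancy rate, and women of childbearing potential must use contraception until 10 weeks after the last injection. A later pregnancy the site learns of is still reportable, since the specific AESI rule can be read as extending the general rule in note h. Passive reporting makes detection less certain, not impossible. For patients who move to commercial product, Section 9.1.1 expressly relies on spontaneous reports.
- **That ending the treatment-emergent period at +14 days departs from the protocol.** It does not. Protocol 9.1.1 sets the same end (Section 11.4.2 writes 14 to 21 days), and Section 11.4.2.1 plans tables of treatment-emergent AESIs. The SAP also has a post-treatment period with its own tables, where a late pregnancy in a female patient can appear if it is recorded within that period.
- **That reported partner pregnancies vanish.** They are absent from one SAP selection. In Protocol 10.5 the sponsor undertakes to include every safety observation in the clinical study report.
- **That partners should be added to the AESI table.** They are not in the safety population (SAP 2.3.2), which is the denominator, so pooling them with patients would produce an invalid percentage.

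All four points stand and limit the size of the problem. They do not remove the mismatch in who is covered, supply an analysis for partner pregnancies, or provide any planned ascertainment after EOT/EOS.

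**Conclusion.** The concern holds in a limited form. Following the SAP as written omits a protocol-defined part of an AESI, with no declared reason and against the SAP's own statement that AESIs follow the amended protocol. Separately, under the current protocol 49 to 56 of the 70 post-dose days carry a reporting duty without a planned means of detection. That range assumes EOT/EOS takes place in the 14 to 21 day window of Section 10.1.2.5, and it does not apply to patients who had the 10-week visit.

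The number of pregnancies affected cannot be derived from the documents and is probably small. All analyses are descriptive and no main estimate changes. The documents do not support calling the count incomplete by construction, or treating the treatment-emergent period as an error. The SAP correction is still worth making because it is specific, nearly free and concerns the primary safety endpoint.

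**What to change.** **SAP 2.1.4.1 and 2.4.5.1.** State that all pregnancies recorded as AESIs will be reported whether or not they fall in the treatment-emergent period. Count female patients with the safety population as denominator. Give partner pregnancies as a separate count or listing outside that denominator. If the sponsor prefers to leave partners out, declare and justify this in SAP 1.5.

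**Protocol.** Reconcile flow chart note h and the triple-asterisk note, Sections 10.1.2.5, 10.4.1.3 and 10.4.2, and the pregnancy-collection part of Appendix K, so that one collection and recording period applies to pregnancy and its status as an AESI is consistent. Which period applies is for the sponsor to decide.

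**Until then,** describe the pregnancy count in the study report as passively reported after EOT/EOS, and note that some patients enrolled under the original protocol had a 10-week visit.

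**Cost.** One extra listing and a wording change in the SAP. The protocol wording needs an amendment with ethics committee approval. Partner data remain subject to the partner's consent and local permission, as the protocol already requires.

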#### **10.4.1.4 Local injection site reactions (non-allergic or allergic not requiring consultation)**

Local injection site reactions that are considered non-allergic (eg, local injection site reactions related to mechanics of injection) or allergic but not requiring consultation with another physician are not considered as AESIs.

The definition of local injection site reactions, the reporting time frame, and the corresponding complementary forms in the e-CRF to be filled are summarized in [Appendix E](#).

#### **10.4.1.5 Device Deficiency**

- A device Deficiency is any inadequacy related to the identity, quality, durability, reliability, safety or performance of the medical device including malfunctions, use errors, and inadequate labeling.
- Product Complaints (PC):
  - Product Complaints is defined as any written, electronic, or oral communication that alleges deficiencies related to the identity, quality, durability, reliability, safety, efficacy or performance of a product after it is released for distribution. Patients will be instructed to contact their site for any questions or difficulties.
- All product complaints (PC) must be reported on a product complaint form when there is a reason to suspect a problem with the device.
- In case of a PC associated with the occurrence of an AE, the AE must be documented on an AE page in the CRF.
- In the case of a PC associated with the occurrence of a SAE, the SAE must be reported as in [Section 10.4.3](#) in accordance with the serious adverse event reporting procedures.

#### **10.4.2 General guidelines for reporting adverse events (and product complaints)**

- All AEs, regardless of seriousness or relationship to investigational medical product (IMP)/ non investigational medical product (NIMP), spanning from the signature of the informed consent form until the end of the study as defined by the protocol for that patient, are to be recorded on the corresponding page(s) or screen(s) of the CRF.
- All products complaints associated or not to an AE are to be recorded immediately on the corresponding products (study medical device) complaints pages and reported to local Complaint Service immediately (within 24 hours).

- Whenever possible, diagnosis or single syndrome should be reported instead of symptoms. The Investigator should specify the date of onset, intensity, action taken with respect to IMP, corrective treatment/therapy given, additional investigations performed, outcome, and his/her opinion as to whether there is a reasonable possibility that the AE was caused by the IMP or by the study procedure(s).
- The Investigator should take appropriate measures to follow all AEs until clinical recovery is complete and laboratory results have returned to normal, or until progression has been stabilized, or until death, in order to ensure the safety of the patients. This may imply that observations will continue beyond the last planned visit per protocol, and that additional investigations may be requested by the monitoring team up to as noticed by the Sponsor.
- Patients who experience an ongoing SAE or an AESI, at the prespecified study end-date, should be followed until resolution, stabilization, or death and related data will be collected. The duration of post study follow-up and reporting of AEs will be specified (eg, until recovery).
- When treatment is prematurely discontinued, the patient will have an EOT (=EOS) visit at least 2 weeks after the last study treatment injection unless there is an AE to be followed until final outcome and related data will be collected.
- Laboratory or vital signs are to be recorded as AEs only if:
  - Symptomatic and/or,
  - Requiring either corrective treatment or consultation, and/or,
  - Leading to IMP discontinuation or modification of dosing, and/or,
  - Fulfilling a seriousness criterion, and/or,
  - Defined as an AESI.

Instructions for AE reporting are summarized in [Appendix E](#).

- Adverse event (injection site reactions) recorded in patient's questionnaire:  
The Investigator must compare the injection site reaction information recorded by the patient in the SIAQ to the information recorded in patient diaries. Based on his/her clinical assessment the investigator would complete an adverse event, when required.

